5. STUDY DESIGN

5.1. Overall Design

This study will be a randomised, double-blind (sponsor open), placebo-controlled, three part study of oral administration of GSK3358699 in healthy male participants. Part A will be a single ascending dose crossover design in two interlocking cohorts of participants (Cohorts 1 and 2). Part B will be a single dose, open-label two-way crossover study with GSK3358699 administered under fed and fasted conditions in a further cohort of participants (Cohort 3). Part C is planned to be a repeat dose design in 5 sequential cohorts of participants (Cohorts 4-8).

[figure not shown]
All participants in Part A, Part B and Part C of the study will attend a screening visit within 35 days prior to their first dose (with the exception of Cohort 8 where the screening visit will be within 45 days prior to their first dose) and a follow up visit within 7-14 days of their last dose. A second follow up visit will also be conducted approximately 5 weeks after the last dose for those participants in cohorts where challenges and blisters are being administered. If warranted, additional follow-up visits may be scheduled.

5.1.1. Part A

5.1.1.1. Part A Single Ascending Doses – Cohort 1 and Cohort 2:

In the Part A dose escalation phase (treatment Periods 1-3), there will be two interlocking cohorts (Cohorts 1 and 2) each with 9 healthy participants. Each participant will receive a maximum of 2 single ascending oral doses of GSK3358699 and 1 placebo dose. At each dose level, GSK3358699 and placebo will be administered in a 2:1 ratio, within each Period, according to the randomisation schedule, in a blinded manner. Up to a maximum of 6 dose levels will be studied in total in Part A as illustrated in Figure 1 below.

Figure 1 Part A Schematic Planned Single Ascending Doses and LPS / GM-CSF challenges

Participants who are enrolled in the dose escalation treatment Periods of Part A may choose to only take part in the dose escalation treatment Periods 1-3, or may choose to also take part in the challenge treatment Period (Period 4) as detailed in Section 5.1.1.2. If a participant chooses to participate in the dose escalation treatment Periods 1-3 only, or does not (at screening) meet the eligibility criteria specific to challenges (treatment Period 4), a new participant will be recruited for treatment Period 4 only and will be regarded as a replacement subject.

During each treatment Period, participants in an individual cohort will be admitted to the clinical unit on Day -1 and will remain there until completion of all assessments on Day 3 (at approximately 48 hours post-dose). Participants will then be discharged from the unit.

Staggering of the first two participants (sentinel dosing) will be implemented in each cohort in each treatment Period for this single dose phase. No participant will be a sentinel participant more than once. On Day 1, one of the two participants will receive the active dose and the other will receive placebo. Assuming adequate safety from these two participants over approximately 48 hrs post-dose, the remaining participants in the cohort can then be dosed from the morning of Day 2.

Data will be reviewed between each treatment Period, and hence dose level, and there will be a minimum 14 days between the start of dosing, (ie dosing of sentinel participants) in Cohort 1 and Cohort 2 in each treatment Period. The decision to proceed to the next dose level of GSK3358699 will be made at a Dose Escalation Committee (DEC) meeting based on:

• assessment of safety, measurable plasma GSK3358699 PK concentrations and derived PK parameters and TE data obtained in a minimum of 6 participants (a minimum of 48 hours post-dose) in the most recently dosed group of subjects. Individual safety data (AEs, laboratory safety tests, ECGs and vital signs) will be reviewed.

• evaluation of all available safety, tolerability, PK, and PD data accumulated from preceding dose levels.

Safety stopping criteria will be strictly applied, precise details of these criteria can be found in Section 8. In addition, specific PK and PD stopping criteria will apply to this FTIH study:

- Dose escalation will be halted if the mean cohort exposure exceeds or is predicted to exceed a *GSK3358699 C_{max} of 42 ng/ml or a total daily GSK3358699 AUC of 255 ng/ml.h*, which are the predicted exposures of the planned maximum dose of 45 mg.
- Individuals in each cohort will be monitored throughout the study. If 2 or more participants in a given cohort at the same dose level exceed C_{max} of 42 ng/ml or total daily AUC of 255 ng/ml.h, dose escalation will be halted.
- Based on the PD of GSK3358699, dose escalation will be halted if mean target engagement within a cohort, as measured by MCP-1 and TNF inhibition in participant blood stimulated *ex vivo* with LPS, exceeds or is predicted to exceed the desired profile: *maintenance of* \geq 90% *MCP-1 and TNF inhibition for a minimum of 12 hours post dose relative to baseline*.
- Additionally, if the PD effect of GSK3358699 appears to have become saturated over the course of 2 consecutive dose levels, dose escalation will be halted.

Furthermore, throughout all parts of the study, either a population PK model or the results of a non-compartmental analysis will be used to help inform the choice of the next dose level as part of dose escalation discussions. For either approach, it is planned that the 95th percentile for the predicted total daily AUC values will not exceed 1/3 of the mean AUC observed at the cynomolgus monkey NOAEL and the 95th percentile of the predicted 1/3 of the mean C_{max} observed at the cynomolgus monkey NOAEL.

Further details of the DEC remit are provided in Section 12.3 and in the Dose Escalation Plan (DEP). This plan outlines how the study team will ensure data integrity used in dose selection decisions by performing clinical data review and appropriate quality control of data prior to making dose selection decisions, as well as outlining the responsibilities of the investigators and site staff for reporting safety data, participation during dose escalation meetings, and confirmation that the data used for dose escalation are accurate and complete.

Further information on dose decisions / modifications is provided in Section 7.2.

5.1.1.2. Part A LPS or GM-CSF challenge with cantharidin-induced blisters – Cohort 1 and Cohort 2:

Upon conclusion of the dose escalation phase of Part A, an additional dosing Period (treatment Period 4) will be included. Eligible participants in both cohorts will attend the clinic for outpatient visits, on Day -10 (\pm 3 days) to have control blisters induced on the

forearm (0.2% cantharidin), and will have a blister sample taken at approximately 48hrs post-blister induction. Participants in Cohort 1 will be administered an IV *in vivo* LPS challenge at a dose of 0.75 ng/kg following treatment with GSK3358699 or placebo and will then have blisters induced on the forearm (0.2% cantharidin) approximately 20 minutes after the challenge. Similarly, participants in Cohort 2 will be administered 60 μ g/m² *in vivo* GM-CSF challenge as an IV infusion following treatment with GSK3358699 or placebo and will then have blisters induced on the forearm (0.2% cantharidin) approximately 20 minutes after the challenge. Similarly, participants in Cohort 2 will be administered 60 μ g/m² *in vivo* GM-CSF challenge as an IV infusion following treatment with GSK3358699 or placebo and will then have blisters induced on the forearm (using 0.2% cantharidin) approximately 20 minutes after the end of the GM-CSF infusion. Of the nine participants within each cohort, six will receive GSK3358699 and three will receive placebo in treatment Period 4, as per the randomisation schedule.

The duration of treatment Period 4 from Day -1 onwards and the implementation of sentinel dosing will be the same as for each of treatment Periods 1-3. The dose levels of GSK3358699 administered to either cohort in treatment Period 4 will be identical and will be decided by the DEC.

The doses of LPS and GM-CSF to be administered to participants have been defined as part of a clinical enabling study [GlaxoSmithKline Document Number 2016N309726_01 Study ID 207654] and will be administered at the GSK3358699 systemic C_{max} defined from data gathered in treatment Periods 1-3. The dose levels of GSK3358699 administered to either cohort in treatment Period 4 will be identical. This will be a single dose of GSK3358699 that is within the range investigated in treatment Periods 1-3 of Part A and the decision on the dose level will be made by the DEC based on all available safety, tolerability, PK and PD data from treatment Periods 1-3.

The *in vivo* challenges included in treatment Period 4 will act as a pre-determinant to their inclusion in Part C. That is, if GSK3358699 treatment does not robustly inhibit production of inflammatory mediators and leukocyte activation following either low dose *in vivo* LPS or GM-CSF challenges and blisters in Part A, the same challenge will not be investigated in Part C. Inclusion of challenges in Part C will be decided once all the data has been generated from treatment Period 4 in Part A, and the criteria will be specific for each challenge. Inclusion of the challenges in Part C will be based on inhibition of multiple inflammatory biomarkers which may include, but are not limited to, TNF, IL-6, MCP-1 and CRP for the LPS challenge, leukocyte activation markers, thymus and activation regulated chemokine (TARC) and Macrophage-Derived Chemokine (MDC) for the GM-CSF challenge, and leukocyte counts, interferon gamma-induced protein-10 (IP-10), MMP-9, transforming growth factor (TGF)- β and leukocyte activation markers for the cantharidin-induced blisters.

5.1.1.3. Part A Dose Escalation / Challenge Total Duration:

There will be a minimum of 14 days between each dosing in Cohort 1 and Cohort 2 to ensure that appropriate dose decisions can be made during the dose escalation phase. This results in a minimum 28 day washout Period between dosing in each treatment Period for a particular cohort (including between treatment Periods 3 and 4).

The total duration of this part of the study for each participant, including screening and follow-up, is approximately 19 weeks for participants taking part in all three dose escalation treatment Periods and 23 weeks if a participant takes part in all four treatment

[figure not shown]
Periods. For replacement participants only taking part in the challenge treatment Period (treatment Period 4), approximate study duration is 10 weeks.

5.1.2. Part B Food Effect - Cohort 3

In Part B there will be one cohort of 6 participants (Cohort 3), taking part in a two-way crossover study as per the schematic in Figure 2. Each participant will receive a single oral dose of GSK3358699 under fed conditions in one of the two treatment Periods and under fasted conditions in the other treatment Period, according to the randomisation schedule.

Part B will only be conducted after completion of the dose escalation phase of Part A and may be conducted in parallel with Part C.

Figure 2 Part B Food Effect - Cohort 3

The dose level chosen for Part B will be a dose level within the range already evaluated in the dose escalation part of the study (Part A) and one in which, based on *in silico* modelling, the maximum exposure is estimated to not exceed the maximum threshold allowed in this protocol (see Section 7.2). following either fed or fasted administration. The decision on the dose level of GSK3358699 to be administered in Part B will be made by the DEC.

During each treatment Period participants will be admitted to the clinical unit on Day -1 and will remain there until completion of all assessments on Day 3 (at approximately 48 hours post-dose). Participants will then be discharged from the unit.

[figure not shown]
There will be a minimum of 14 days between each dose.

The total duration of this part of the study for each participant, including screening and follow-up, is approximately 9 weeks.

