12-Lead ECGs	x	x	x					x	x		x	x	x	x	See separate Period 4 Schedule of Activities	x		12 Lead ECGs will be performed in triplicate at screening, Day-1, Day 1 pre- dose, Day 2 and Day 3. Single ECGs will be performed at other time points and if any cardiac symptoms are experienced. ECGs to be performed prior to blood draws and dosing where these fall at the same nominal time.
Telemetry			<==										===>		dule			from 1 h pre-dose to 24 h post-dose
Holter monitoring (24 hours)	Х														of Activ			If a participant is rescreened the Holter will not need to be repeated.
HIV, Hep B, Hep C	Х														ities			
Haematology	х	х									х		x	x		x		Fasted screening samples. 24 and 48 hour samples will be taken prior to participants receiving breakfast
Coagulation	х										х		x	x		х		Fasted screening samples. 24 and 48 hour samples will be taken prior to participants receiving breakfast

CONFIDENTIAL

Procedure	Screening (up to 35 Days prior to Day 1)					-	Treatm Da	ient Pe ay 1	eriod 1	-3			Day 2	Day 3	Treatment Period 4	Follow-up 1 (7-14 days post-last dose)	Follow-up 2 (5 we dose ± 3 c	Notes
	Days prior to	Day -1	Pre-dose	0 h	15 mins	30 mins	1 h	2 h	4 h	6 h	4 8	12 h	24 h	48 h	eriod 4	lays post-last	5 weeks after last ⊦ 3 days)	The 2nd follow up visit is only required for those participants where challenges are being administered and blisters induced i.e. treatment period 4
Clinical Chemistry	х	х									х		x	Х		х		Fasted screening samples. 24 and 48 hour samples will be taken prior to participants
Urinalysis	х	х									х		x	х		х		Fasted screening samples. 24 and 48 hour samples will be taken prior to participants receiving breakfast
Drug / Alcohol Test	Х	Х																
Urine Cotinine	Х	Х																
Visual forearm check (cosmetic assessment or blister healing where appropriate)	X	Х														X	X	 Visual forearm checks are only required if participant is scheduled to take part in treatment period 4. Details of checks: Screening check prior to first treatment period (cosmetic assessment) Day -1 check in treatment Period 3 only. Between Day -1 and Day 2 (ie 48 hour window) (cosmetic assessment) Period 4 (cosmetic assessment) Period 4 (cosmetic assessment and blister healing). For further detail on time points in Period 4 see Section 2.1.1. Follow-up visits 1 and 2 (blister healing)

CONFIDENTIAL

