9.4.4. Vital Signs

- Tympanic temperature, heart rate, respiratory rate, and blood pressure will be assessed.
- Vital signs measurements are to be taken before blood collection for laboratory tests.
- Tympanic temperature and respiratory rate will be taken as single measurements at the timepoints detailed in the SoA.
- Blood pressure and pulse measurements will be assessed in a semi-supine position with a completely automated device. Manual techniques will be used only if an automated device is not available.
- Blood pressure and pulse measurements should be preceded by at least 5 minutes of rest for the participant in a quiet setting, in a semi-supine position, without distractions (eg, television, cell phones).
- In Part A and Part B, blood pressure and pulse measurements will be performed as follows.
 - Day -1, Day 1 pre-dose, 24 h and 48 h post-dose: triplicate measurements
 - Day 1 post-dose: single measurements throughout except for:
 - GSK3358699 C_{max} timepoint; triplicate measurement
 - For 12 hours post-LPS challenge: triplicate measurement

- In Part C (Cohorts 4 and 8), blood pressure and pulse measurements will be performed as follows:
 - Day 1 to Day 13: triplicate measurements
 - Day 14 pre-dose, Day 15 and Day 16: triplicate measurements
 - Day 14 post-dose: single measurements throughout except for:
 - GSK3358699 approximate C_{max} timepoint; triplicate measurement
 - For 12 hours post-LPS challenge: triplicate measurement
- In Part C (Cohorts 5 7), blood pressure and pulse measurements will be performed as follows:
 - Day 1 to Day 13: triplicate measurements
 - Day 14 pre-dose, Day 15 and Day 16: triplicate measurements
 - Day 14 post-dose: single measurements throughout except for:
 - GSK3358699 approximate Cmax timepoint; triplicate measurement
- At timepoints where triplicate measurements of pulse and blood pressure are required, 3 consecutive readings will be recorded at intervals of at least 1 minute.

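### The Part A sentinel rule asks for about 48 h of safety data but lets the other seven participants be dosed on Day 2, which is 24 h

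*Protocol*

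**What the plan says.** Protocol 5.1.1.1 staggers the first two participants in each cohort and each treatment Period: "On Day 1, one of the two participants will receive the active dose and the other will receive placebo". If their safety is adequate "over approximately 48 hrs post-dose, the remaining participants in the cohort can then be dosed from the morning of Day 2".

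The same section fixes where 48 h falls. Participants stay in the unit and "will remain there until completion of all assessments on Day 3 (at approximately 48 hours post-dose").

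The Part A schedule (Protocol 2.1) heads Day 2 as 24 h and Day 3 as 48 h. Two other places use the same mapping:

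- the ECG note in 2.1: "performed in triplicate at screening, Day-1, Day 1 pre- dose, Day 2 and Day 3"
- the vital signs rule in 9.4.4: "Day -1, Day 1 pre-dose, 24 h and 48 h post-dose: triplicate measurements"

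The rule also reaches the challenge period. Section 5.1.1.2 says that in Period 4 "the implementation of sentinel dosing will be the same as for each of treatment Periods 1-3".

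The parallel statements give 48 h with no day label: SAP 2.3 for Part A, and Protocol 5.1.3.2 and 5.1.3.3 for Part C.

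**The concern.** A sentinel rule exists to hold back the rest of the cohort until the first active participant has been observed for a set time. Here the set time and the earliest permitted day do not agree, and the day label is the easier of the two to schedule against.

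If Day 2 is followed, the rest of the cohort receives the same dose when only one person has taken it, about 24 h earlier. His telemetry, which runs "from 1 h pre-dose to 24 h post-dose", is only just ending. Still to come are his 48 h triplicate ECG, triplicate vital signs, brief physical examination and laboratory tests. The 48 h intracellular PK sample is also outstanding, and Protocol 5.4 describes the intracellular kinetics of the active metabolite as hard to predict. That is a reason to value the second day of observation.

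**Working it through.** No statistical calculation applies. The check is day counting and a head count.

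**Inputs**

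- Sentinels dosed on Day 1, one active and one placebo (Protocol 5.1.1.1).
- Required observation about 48 h; rest of cohort from the morning of Day 2 (5.1.1.1).
- Nine participants per cohort, 6 active and 3 placebo at each dose level (5.1.1.1, 5.2).
- At least 14 days between sentinel dosing in one cohort and sentinel dosing in the other (5.1.1.1).

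**Elapsed time.** With the dosing day as Day 1, hours elapsed at the same clock time on Day d are (d − 1) × 24.

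- Morning of Day 2: (2 − 1) × 24 = 24 h
- Morning of Day 3: (3 − 1) × 24 = 48 h
- Shortfall if Day 2 is used: 48 − 24 = 24 h, half the stated window

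Counting the dosing day as Day 0 would put 48 h on Day 2, but the paragraph itself calls the sentinel dosing day Day 1.

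**Who is affected per dose level**

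- Remaining participants: 9 − 2 = 7
- On active: 6 − 1 = 5
- On placebo: 3 − 1 = 2

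**Which half of the sentence is the slip.** Three places point to 48 h:

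- SAP 2.3 restates the Part A rule as the first 48 h and omits Day 2.
- Both Part C sentinel rules use the first 48 h of dosing.
- The Dose Escalation Committee needs at least 48 h of post-dose data before escalating (5.1.1.1).

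No other sentinel text supports 24 h.

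**Room in the timetable.** The 14-day gap runs from sentinel dosing, so the next cohort's sentinels are dosed on Day 1 + 14 = Day 15 at the earliest.

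| Rest of cohort dosed | They reach 48 h on | Days before next sentinels |
|---|---|---|
| Day 2 | Day 4 | 15 − 4 = 11 |
| Day 3 | Day 5 | 15 − 5 = 10 |
| Day 4 | Day 6 | 15 − 6 = 9 |

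**The case against.** The strongest reply is that nobody is likely to be harmed by this sentence. Dosing the rest is conditional on 48 h of adequate safety and is only permitted, not required, so a careful reader waits and the Day 2 phrase has no effect. No document shows that a site acted on the earlier time. Cohorts 1 and 2 were complete by Amendment 4: Protocol 7.1 sets the first Part C dose after the Part A challenge periods, and 5.1.3.1 notes that Cohort 4 had started. The SAP (2.1, 2.3) adds that the study stopped early, with Part C dosing only in Cohorts 4 and 5, and it lists no added Part A cohort. This stands, and it limits the practical weight of the point. It does not make the sentence consistent.

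The safety argument also has limits:

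- Protocol 5.4 predicts a systemic half-life of about 3 h, so about 24 / 3 = 8 half-lives have passed by 24 h. The case for the second day rests on the intracellular metabolite and the scheduled 48 h checks.
- Protocol 3.3.1 records four cases of non-sustained ventricular tachycardia, two in Part A. Onset times are not given, causality was not established, and no correlation with measured systemic concentrations was seen. Scheduled Part A telemetry ends at 24 h, so waiting to 48 h adds an ECG but no scheduled rhythm monitoring. These cases give little support for either time.

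Finally, the Amendment 3 history (Protocol 12.8) says the timing text was revised to make clear that 48 h is not an exact timepoint. It can be argued that this leaves the intent open and that the hours, not the day, could be the error. Tolerance around 48 h is reasonable; a full day is beyond it. The parallel rules still favour 48 h.

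**Conclusion.** The concern holds. Protocol 5.1.1.1 states one safety rule with two earliest times 24 h apart, and the word approximately cannot bridge them. Following the day label would halve sentinel observation, from 48 h to 24 h, for seven participants per dose level, five on active.

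The live effect under Amendment 4 is none for Cohorts 1 and 2. For an added Part A cohort, which 5.2 (at most 9 participants) and 7.2 still allow, it is at most seven participants per dose level. Five of those would be on active, assuming the 2:1 ratio and the one-plus-one sentinel pair are kept. Given the SAP's account of early termination, the point now bears mainly on the protocol text as it stands.

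It should be fixed because it is a participant-safety rule, the intended value is clear from the parallel text, and the correction is small. It does not show that anyone was dosed early.

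**What to change.** In Protocol 5.1.1.1, replace the Day 2 phrase with: *from Day 3, once the available sentinel safety data to approximately 48 h post-dose have been reviewed*. Period 4 is corrected through its cross-reference in 5.1.1.2. The Part C rules and SAP 2.3 need no change. If the sponsor did mean Day 2, the window would have to read about 24 h, with a reason for departing from the Part C rule.

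The cost is one phrase and about one day per dose level. The protocol's note that "24 and 48 hour samples will be taken prior to participants receiving breakfast" puts the sentinels' 48 h bloods on the morning of Day 3, and Part A dosing is fasted (6.3.1). A site that chooses to wait for those results could therefore slip to Day 4. Even then the rest of the cohort reaches 48 h nine days before the next sentinels are dosed, so the gap between cohorts is unaffected.

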5.1.3. Part C

Part C of this study intends to investigate doses of GSK3358699 which deliver a robust pharmacodynamic response with adequate safety/tolerability and does not intend to dose escalate beyond the PK and PD stopping criteria detailed in Section 8.

5.1.3.1. Part C Multiple Ascending Doses Cohort 4

Cohort 4 of the study is comprised of 14 participants, taking part in one repeat dose treatment Period as illustrated in Figure 3, and randomised in a 5:2 ratio to receive either GSK3358699 or placebo, according to the randomisation schedule, once daily from Day 1 to Day 14 (note that Cohort 4 was started but not completed due to the temporary halt).

See Section 5.1.3.3. for study design.

5.1.3.2. Part C Multiple Ascending Doses Cohorts 5, 6 and 7

In the multiple ascending dose phase of Part C there are 3 cohorts planned (Cohorts 5-7), each with 18 healthy male participants. Each cohort will take part in one repeat dose treatment Period as illustrated in Figure 3. The participants will be randomised in a 1:1 ratio to receive either GSK3358699 or placebo, according to the randomisation schedule, once daily from Day 1 to Day 14 inclusive.

All participants will be admitted to the clinical unit on the day prior to dosing (Day -1) and will remain in the Unit until after the 48 hour assessments following the Day 14 GSK3358699 / placebo dose administration have been completed (Day 16). Participants will then be discharged from the unit.

Staggering of the first two participants (sentinel dosing) will be implemented for each cohort where a new GSK3358699 dose regimen is being tested. On Day 1, one of the two participants will receive the active dose and the other will receive placebo. Assuming adequate safety from these two participants after the first 48 hours of dosing, the

remaining participants in the cohort can then be dosed. If a sentinel subject withdraws after the first 48 hours, the remainder of the cohort can still be dosed.

The decision on the dose level of GSK3358699 to be administered in Cohort 5 will be made at a DEC meeting based on all available safety, tolerability, PK, PD and TE data accumulated from Part A of the study, Part C Cohort 4, and the dose modification / stopping criteria detailed in Section 7.2 and Section 8.

The decision on the dose level of GSK3358699 for the next repeat dose cohort (Cohort 6 onwards) will be made at a DEC meeting following completion of a minimum 14 days dosing in no fewer than 12 participants in the current repeat dose cohort and will be based on:

- assessment of all available safety, tolerability, PK, PD and TE data accumulated from Part A of the study.
- assessment of safety, plasma GSK3358699 PK concentrations and TE data obtained in a minimum of 12 participants in the most recently dosed group of subjects. Individual safety data (AEs, laboratory safety tests, ECGs and vital signs) will be reviewed.
- evaluation of all available safety, tolerability, PK, PD and TE data accumulated from the previous repeat dose cohorts.

As part of this decision making process, the DEC may decide to escalate or de-escalate the dose. Safety, PK and PD stopping criteria will be strictly applied as in Part A of the study. Details of these criteria can be found in Section 8.

Further information on dose decisions / modifications is provided in Section 7.2.

The total duration of the multiple ascending dose phase of Part C, including screening and follow-up, is approximately 10 weeks for each participant in Cohorts 5 - 7.

5.1.3.3. Part C Repeat Dosing Followed by LPS or GM-CSF Challenge with Cantharidin-Induced Blisters Cohort 4 and 8

Upon conclusion of the multiple ascending dose phase of Part C (Cohorts 5 - 7), an additional Cohort (Cohort 8) is planned to be included (Figure 3). This cohort will be comprised of 20 participants, taking part in one repeat dose treatment period.

Participants will be randomised in a 1:1 ratio to receive GSK3358699 or placebo once daily for up to 14 days. The actual duration of dosing will be decided by the DEC and will not exceed 14 consecutive days.

Participants will attend the clinic for outpatient visits, on Day -10 (\pm 3 days), to have control blisters induced on the forearm (0.2% cantharidin) and will have a blister sample taken at a timepoint at approximately 48 hours post-blister induction.

On the final day of dosing, an IV *in vivo* LPS challenge at a dose of 0.75 ng/kg or a 60 μ g/m² GM-CSF challenge as an IV infusion will be administered as per the timepoints detailed in the SoA (Section 2.4.1), followed by blister induction (as described in Section 5.1.1.2 Part A, treatment Period 4).

Half the participants will be randomised to receive the LPS challenge and half will receive the GM-CSF challenge. In Cohort 4, of the 7 participants receiving each challenge, 5 will be randomised to receive GSK3358699 and 2 to receive placebo at the start of the cohort. In Cohort 8, of the 10 participants receiving each challenge, it is planned that 5 will be randomised to receive GSK3358699 and 5 to receive placebo.

The randomisation ratio of active to placebo for Cohort 8 and any subsequent additional cohorts may be altered by the DEC based on all available safety, PK and PD data following the conclusion of Cohort 7.

Data from Part A of this study and from Cohorts 4 - 7 in Part C will be used to confirm the decision for inclusion of the challenges in Part C Cohort 8. The decision will be made by the DEC.

All participants will be admitted to the clinical unit on the day prior to dosing (Day -1) and will remain in the Unit until after the 48 hour assessments following the final day of GSK3358699 / placebo dosing and challenge administration have been completed. Participants will then be discharged from the unit.

Staggering of the first two participants (sentinel dosing) will be implemented. On Day 1, one of the two participants will receive the active dose and the other will receive placebo. Assuming adequate safety from these two participants after the first 48 hours of dosing, the remaining participants in the cohort can then be dosed. If a sentinel subject withdraws after the first 48 hours, the remainder of the cohort can still be dosed and the challenges administered. The staggering of the participants will be such that the post-challenge safety data from previous participants can be reviewed prior to further participants receiving challenges. The decision to administer a challenge to a participant will be based on that individual's safety profile as well as continuous review of safety/tolerability of the challenges.

The decision on the dose level of GSK3358699 to be administered in Cohort 4 will be made at a DEC meeting based on all available safety, tolerability, PK, PD and TE data accumulated from Part A of the study and the dose modification / stopping criteria detailed in Section 7.2 and Section 8.

The decision on the dose level of GSK3358699 to be administered in Cohort 8 will be made at a DEC meeting based on all available safety, tolerability, PK, PD and TE data accumulated from Part A of the study, the previous Part C cohorts, and the dose modification / stopping criteria detailed in Section 7.2 and Section 8.

As part of this decision making process, the DEC may decide to escalate or de-escalate the dose. Safety, PK and PD stopping criteria will be strictly applied as in Part A of the study. Details of these criteria can be found in Section 8.

Further information on dose decisions / modifications is provided in Section 7.2. This includes any potential changes to the randomisation and administration and timing of challenge agents, as well as any changes related to the dose levels or dosing regimen of GSK3358699.

The total duration of Part C of the study, including screening and follow-up, is approximately 12 weeks for participants in Cohort 4 and approximately 14 weeks for participants in Cohort 8.

